1.0 Research Design

1.1 Purpose/Specific Aims

A. Objectives

Although many children diagnosed with ASD make significant progress in learning and their cognitive skills improve with applied behavior analysis (ABA) and other teaching techniques, there are a significant number who show an absence or a plateau in various skills. Deficits in executive functioning are likely to be involved in many of these cognitive and learning disabilities due to poor functioning of the prefrontal cortex. Currently, the use of biological methods for improving learning and cognition is largely unexplored in research and practice.

Transcranial Direct Current Stimulation (tDCS) is a low-level electrical neurostimulation that has been used for various indications for decades and with no serious side effects. There is accumulating evidence that tDCS is effective in treating the comorbidities as well as the core symptoms of ASD. tDCS is most effective when used simultaneously with an active intervention. In this study, we will extract the effects of tDCS alone and in combination with ABA on the executive functioning skills and the core symptoms of ASD and monitor the results using an objective neurophysiological test (EEG).

The objective of this study is to pilot the use of transcranial direct current stimulation (tDCS) in combination with behavioral intervention to improve the acquisition of educational programs for students with ASD.

We will be working with students in structured programs that provide comprehensive applied behavior analysis (ABA) with objective interventions and employ data-based evidence to guide the educational programs, either in-school or in-home. tDCS has been used for various indications over a couple of decades and has been shown to be very safe (30,000 treatment episodes yielded no serious side effects) and has been well-tolerated by children with ASD. The mechanism of tDCS's effectiveness is not clear, however animal studies show that tDCS can stimulate the flow of calcium ions through channels in the astrocytes, activating them, and facilitating their role in synapse formation and therefore learning.

B. Hypotheses / Research Question(s)

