Aim #1: To pilot the use of tDCS to children with ASD enrolled in ABA programs. We intend to provide the stimulation during the ABA therapy sessions focused on preselected cognitive programs and measure the outcome via a standardized instrument, and we will also use discrete acquisition data compiled as part of the students programming.

There is accumulation evidence that tDCS is effective in treating the core symptoms of ASD as well as co-morbidities, but there are still gaps in our knowledge. Nearly all the existing studies were done on high functioning adults with ASD. The larger double-blind studies utilized general ASD outcome measures and specific comorbid symptoms were not examined, especially in combination with evidence-based intervention in a natural environment setting. This research study further our understanding of the benefits of tDCS in treating the comorbidities and core symptoms in children with ASD.

Aim #2: To evaluate a biomarker of brain complexity at various points (before, during, and after the treatment) obtained through EEG measurements. We will use portable EEG devices which can be used in the therapy session. We hypothesize that through this treatment, circuits will be made more functional and this will be associated with increased complexity measured on the EEG, which has been shown to be associated with typical functioning when compared to ASD brainwaves.

EEG data will be obtained and analyzed for complexity with a unique algorithm previously successful in separating ASD from controls and predicting outcome in children as young as 3 months old ([name], Tierney et al., 2011; [name], Tager-Flusberg et al., 2018). The question of whether this will be predictive (at baseline) or associated with clinical improvement will be investigated.

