In addition, we will be piloting the use of EEG prior to treatment as a digital biomarker which could predict response to the tDCS, and we will get EEGs before and after each arm of treatment/. We will be using an algorithm which measures EEG complexity and this method has been shown to be highly predictive of ASD from non-ASD in children as early as 3 months of age ([name], Tager-Flusberg et al., 2018). See preliminary data.

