1.3 Research Design and Methods

A. Research Procedures

Study Subjects

Participants will include school-aged children with ASD between the ages 5-12. We selected this age group because a diagnosis is typically made by the age of 5. This age group also allows us to profit from neuroplasticity while avoiding potential variables related to children undergoing puberty. This age group is also likely to be enrolled in intensive ABA programs aimed at executive functioning and social communication intervention. Based on the gender distribution of ASD in the population, we expect that our group will be approximately 75% male. Participants will be recruited from the local New Jersey community, from ABA schools and ABA agencies.

Experimental Design

The study will use a randomized double-blind controlled placebo (sham tDCS) crossover design. The study will involve 5 total months of participation. Participants will be randomized into two groups using a random number generator. They will receive either:

- A) 20 active tDCS stimulation followed by 20 sham stimulation: or
- B) 20 sham stimulation followed by 20 active tDCS stimulation.

Randomization & Blinding

We anticipate recruiting 24 participants in anticipation of 4 subjects dropping out. We will use SAS programming to generate a randomization schedule with a block length of 6 and four blocks. Participants will enter the randomization schedule after consent is obtained and they are assigned a study ID.

002	2	Sham	tDCS
003	2	Sham	tDCS
004	1	tDCS	Sham
005	2	Sham	tDCS
006	1	tDCS	Sham

Block 1 example- there will be four blocks = 24 participants recruited.

[figure not shown]
Subjects 21-24 (to account for drop outs) will receive randomization order of the subject they are replacing but will receive a new study ID. For example if the subject with study ID 004 drops out then subject with study ID0021 will receive randomization schedule 1.

[name] will utilize the generated randomization schedule to provide active tDCS and sham stimulation codes that will be entered into the tDCS device (by the parent) prior to each session. These numeric codes will be random numbers and not distinct to the study group assignment, protecting the blind. Because of her role, [name] will remain unblinded and will not be involved in any assessments. All other study staff, including Drs. [name], [name], and [name], will remain blind. Parents, participants, and ABA providers will also remain blind.

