Desensitization to tDCS headband: Children with ASD may not tolerate wearing the tDCS headband for 20 minutes while engaged in ABA therapy. In order to facilitate tolerance and cooperation, we will provide 2-3 desensitization sessions per day during a week-long period. An eligible participant must be able to wear the headset for the full 20 minutes during the last two desensitization sessions in order to enroll in the study.

Removal of tDCS headband: Despite these desensitization efforts, in a population of children with ASD, it is possible that participants may remove the tDCS headband during stimulation. This has occurred during our preliminary work, especially at 1.5mA (note that we are proposing to use 1.0mA in this study). The tDCS device however can immediately sense the change in impedance and turn itself off automatically. We were able to reinstitute the treatment in a relatively short amount of time (<1 min) and the participant received the full length of treatment. It is unlikely that a short interruption would change the effects of the treatment.

Non-consecutive sessions: We are proposing to stimulate participants during their weekday ABA sessions. It is possible that for a portion of the participants, completing 5-consecutive tDCS sessions during their ABA therapy may not be possible due to participant and/or therapist absence (holidays, illness, etc.). In such cases, we will make up those missed stimulation sessions in order to administer the total number of active and sham tDCS.

Research Timeline -

Please note that the study participant will continue with ABA intervention throughout the entire study.

Enrollment

Week 1-

Daily Living Skills: Each participant will be given the Vineland Adaptive Behavior Scale (VABS-III). It assesses personal and social functioning for those up to 90 years of age, administered to a parent or caregiver using a semi-structured interview format. **The Medical History and Medication History will be obtained.**

Week2-4

Cognitive Profile: Results of cognitive testing (in IEP or psychological report provided by parent). A Leiter 3 cognitive assessment will be administered to study participant if the participant does not have a recent cognitive assessment (within past 3 years). ...

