Nonlinear values derived from Recurrence Quantitative Analysis (RQA) will be computed. RQA is an empirical approach to analyzing time series data that is in principle capable of characterizing all the essential dynamics of a complex system. It has been found to be useful for analyzing "real-world, noisy, high dimensional data" (Webber & Zbilut, 2005). Software for computing recurrence plot statistics is publicly available python package pyRQA 0.1.0 (Marwan, 2012). At least seven of the most commonly used recurrence plot values (RR, DET, LAM, L_max, L_entr, L_mean, and TT) will be computed and used in this study. These values have proven to be potential biomarkers for autism ([name] et al., 2018) and absence epilepsy ([name] et al., 2017) in our previous studies.

EEG analysis will first determine significant group differences between actual and sham tDCS for each of the nonlinear signal features computed. We hypothesize that significant changes will be observed in the nonlinear signal features. A Bonferroni correction will be required for the set of nonlinear measures. In addition to feature comparisons, regression models will be computed using the nonlinear EEG features as input variables and the change in assessment scores as output. Linear regression and machine learning regression models will be used.

Taken together, these analyses will provide the information necessary to determine if tDCS significantly improves the efficacy of behavioral therapy for improving cognitive function in children with ASD. In addition, the usefulness of EEG as a tool for measuring the changes in brain function due to tDCS augmented behavioral therapy will be determined.

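### The regression meant to test whether baseline EEG predicts response to tDCS has an undefined outcome, an unstated EEG time point and no active-versus-sham contrast, so it cannot separate predictive from merely prognostic markers

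*Combined protocol and SAP*

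**What the plan says.** Section 1.2 describes the study as "piloting the use of EEG prior to treatment as a digital biomarker which could predict response to the tDCS". Aim 2 in section 1.1 is a little broader: "The question of whether this will be predictive (at baseline) or associated with clinical improvement will be investigated".

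The matching analysis is in section 6.1, under EEG as a Biomarker for Treatment Outcome. It has two parts.

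- A comparison of conditions on the EEG itself: "EEG analysis will first determine significant group differences between actual and sham tDCS for each of the nonlinear signal features computed".
- Regression models "using the nonlinear EEG features as input variables and the change in assessment scores as output", with the sole further detail that "Linear regression and machine learning regression models will be used".

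The regression text names no phase, treatment condition, feature-by-condition interaction or EEG time point. The schedule has EEG, BRIEF and PDDBI at weeks 4, 8, 12, 16 and 20, so several changes and several EEG inputs would fit the wording.

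On background treatment, section 1.3 says: "Please note that the study participant will continue with ABA intervention throughout the entire study". On design, it says: "The study will use a randomized double-blind controlled placebo (sham tDCS) crossover design".

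**The concern.** To say that a marker predicts response to tDCS, one must show that it relates to the effect of tDCS, that is, to active relative to sham. A score change over one phase also contains progress under ABA, maturation and regression to the mean, and these occur under sham as well. Section 1.1 itself expects many children to progress with ABA while others plateau. That variation between children is what a prognostic marker would pick up.

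Sections 1.5 and 1.6 give the long-term purpose as gathering EEG biomarker data to justify an adequately powered trial. A prognostic feature carried forward as a predictive one would select children who improve on sham too. This is a question of which effect is estimated. It is separate from how many features are tested and from overfitting.

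**Working it through.** The plan gives no power, error rate or effect size for the EEG prediction, so there is no figure to reproduce.

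**1. What each choice of outcome estimates.** For child *i* with baseline marker *x*, write the phase changes as

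- active change = period effect + τ + (β + γ)x + error
- sham change = period effect + βx + error

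Here β is the marker's relation to ordinary progress (prognostic), γ is its relation to the tDCS effect (predictive), and τ is the average tDCS effect. The slope on *x* is then:

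- active-phase change: β + γ
- both phases pooled: β + γ/2
- active minus sham: γ

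Only the last answers the question in section 1.2. The period effect enters the difference with opposite sign in the two sequences, so a sequence term is needed to remove it.

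**2. Whether another part of the plan supplies the contrast.** The active-versus-sham EEG comparison in section 6.1 treats EEG features as outcomes. The t-test on within-subject differences concerns BRIEF and PDDBI means. The Bonferroni statement concerns multiplicity. None of these puts condition into the regression.

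**3. Illustrative size.** Inputs from the documents: 20 completers (section 4.3) and P < 0.05 (section 6.1, taken as two-sided). Assumed, because the documents give nothing: the marker's correlation ρ with background progress, and the share of the phase-change variance due to that progress. The true γ is 0. The marker's correlation with a phase change is ρ × √share; for example 0.5 × √0.5 = 0.35. Simulation (6,000 to 40,000 trials per setting; ranges show spread over repeated runs) gave these rates of declaring the marker significant against active-phase change:

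| Share of variance | ρ = 0.3 | ρ = 0.5 | ρ = 0.7 |
|---|---|---|---|
| 10% | 7% | 10% | 15–16% |
| 25% | 9% | 18–19% | 33–34% |
| 50% | 14–15% | 34–35% | 63% |
| 70% | 18–19% | 46–47% | 81% |

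The rates against sham-phase change are essentially the same, which shows that the finding is not about tDCS. Against active minus sham, the rate is about 5% in every cell.

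Section 6.1 names four nonlinear measures and at least seven recurrence values. If a Bonferroni correction for these 11 extended to the regression, the threshold would be 0.05/11 = 0.0045. The rates would then be 2%, 9% and 26–27% at a 50% share, and 3%, 15% and 47% at 70%.

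**4. Noise in the difference.** If a single change has variance σ² and a child's two changes correlate *r*, the difference has variance 2σ²(1 − r). It is noisier than one change only if r < 0.5. In the model above *r* equals the share. With progress variance 1, a 50% share gives variance 2 for both. A 70% share gives 1/0.7 = 1.43 for one change and 2 × (1/0.7 − 1) = 0.86 for the difference.

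**5. Power of the right contrast.** With 20 children, a sequence term and independent residuals in the two phases, power for a true γ of 0.3, 0.5, 0.7 or 1.0 residual SD per marker SD is about 13%, 29%, 50% and 77%.

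**The case against.** The strongest reply is that section 6.1 is silent and has not made a wrong choice. Its treatment test uses within-subject differences, so the outcome could be meant as active minus sham. It also does not say that the regression inputs are baseline features; that link comes from sections 1.1 and 1.2. Aim 2 asks about association with improvement as well, and a regression on change can address that. This stands. A reader might infer that the plan has chosen active-phase change and set sham aside, or that a false biomarker will be reported. The documents support neither: the outcome is undefined, and false prediction needs a feature that correlates with ABA progress, for which they give no figure.

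The silence still leaves the predictive question without a matching analysis. Section 6.1 also speaks of changes over time in either condition, so the active-minus-sham reading is not the natural default.

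Two further objections stand in part. The simulated rates rest on assumed inputs and one unadjusted marker, whereas the plan has many features and machine-learning models. And a raw active-minus-sham difference is not enough, because it carries the period effect. Regression to the mean from Baseline 1 would also fall mainly in the first period and so would not simply cancel within a child.

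That this is a pilot argues for an exploratory label, but not for estimating a different effect.

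**Conclusion.** The point holds as a gap between question and analysis. As written, the regression does not specify an effect that answers whether baseline EEG predicts response to tDCS, and a within-phase or pooled change would not distinguish a prognostic from a predictive marker. That conclusion follows from the slopes in step 1 and needs no assumed number beyond β not being zero.

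The size is illustrative: about 14% to 81% false prediction at 50% to 70% background share and ρ of 0.3 to 0.7, less with a smaller share or a Bonferroni correction, against about 5% for the active-minus-sham outcome. The point affects the interpretation of Aim 2 and leaves the primary BRIEF comparison untouched. It should be corrected before analysis.

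**What to change.** In section 6.1:

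- For the predictive question, regress each child's active-phase change minus sham-phase change on Baseline 1 EEG features, with a term for treatment sequence. Equivalently, fit a mixed model with period, condition and a baseline-feature-by-condition interaction. State the start and end time points of each change, and label the analysis exploratory.
- If active-phase change alone is also modelled, run the same model on sham-phase change and describe any feature appearing in both as prognostic.
- Regressions of score change on EEG change may stay for the association part of Aim 2, but should not be reported as predicting tDCS response.
- State whether the Bonferroni correction extends to the regressions.

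The cost is SAP wording; the crossover already gives each completer both changes, and Baseline 1 EEG is scheduled for all. The downside is low power with 20 completers and one degree of freedom spent on sequence. Whether precision is lost relative to a single change depends on the within-child correlation of the two changes, which the trial can estimate and report.

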6.2 Data Security and Quality 6.2a Training and Safeguards

All study personnel will receive training prior to start date of the study. There will be a kick-off meeting with the PI and Co PIs as well as research assistants. All study-related staff will receive data safety and confidentiality training. Research Staff will ensure the identity of the participants and data collected remains confidential. The following safeguards will be implemented to maintain human subject confidentiality:

- ➤ Each participant will be given a unique study identification number. These identifiers will be transcribed into a logbook with corresponding subject name. The logbook will be kept in a locked cabinet in the Pl's office. In addition an excel spread sheet will be kept i(n the research folder of the restricted pediatric drive) with the study ID and subject name. Only the study coordinator and research assistants/PI will have access to this drive.
- Only the personal study ID will be used on data collection sheets where clinical data will be transcribed. Data collection sheets may be stored in the subject's binders until entered into RedCap and then destroyed. The subject folders only have the subject ID
- School reports such as IEP or psychological testing will be reviewed by the study psychologist and research assistants but not copied or stored in research binders. Psychological testing data will be extracted onto data sheets with the participants ID but without personal identifiers.
- Information from the data collection sheets (using only subject unique ID) will be entered into the RedCap database which will be secured with password protection. Data collection sheets may be stored in the subject's binders until entered into RedCap and then destroyed.
- > Subject data will be entered into a password-protected database RedCap Database.
- Subject's parent and legal guardian will complete behavioral data (i.e., questionnaires) online through RedCap. Each participant will be emailed a link which opens to a behavioral form with subject ID and no identifiers. Once the form is completed by the family member, it is automatically uploaded to the

RedCap database. Subject parent and legal guardian will not be able to view the database or other subject files.

- Any publication will not include any identification of the study participants.
- The link between the subject unique I. D .and subject names will be destroyed after the completion of data collection and data analysis.
- > The study data will be kept in a RedCap database for a minimum of 6 years after study closure or publication of the data.
- Confidential information obtained through written consent will be held exclusively by the study's investigators and will in no way influence the access to and quality of medical care provided.
- The PIs and the study staff will review all data on an ongoing basis for data completeness and accuracy. Data verification will be performed by someone other than the individual originally collecting the data.

6.2b Data Security

- > Study personnel whose responsibilities require access to personal health information will keep the identity of the participants and data related to the study confidential. The data will be stored in a locked cabinet within a locked office. The information on the data collection sheet will be entered into a password-protected database RedCap Database with access limited to the study staff. The data will be collected and processed with adequate precautions to ensure confidentiality and compliance with applicable data privacy protection laws and regulations. The REDCap application is a secure web application for building and managing online databases. REDCap can be installed for compliance with such standards as HIPAA, 21 CFR Part 11, FISMA and international standards. Access to the computerized data will be strictly limited to study investigators approved by the Institutional Review Board, except as required by law.
- For questionnaires that are collected and transmitted through the internet, the participant parent or legally acceptable representative will have the participant's assigned code, rather than name, when submitting the data. There are no foreseeable risks to participation except for the remote possibility that the responder's email or IP address would be inadvertently disclosed.

6.3 Data and Safety Monitoring Our study meets the NIMH definition of minimal risk.

6.3aData/Safety Monitoring Plan

Our study meets the NIMH definition of minimal risk (i.e., the probability and magnitude of harm or discomfort anticipated in the research risks is no more than minimal risk (SEE ATTACHMENT LETTER). Our subjects are Autistic Children who present with unique communication and sensory challenges. Therefore, we have included the data and safety monitoring procedures to be followed by the research team. The PI will ensure surveillance protections are in place to ensure safety and to report any adverse events to the IRB promptly.

- Prior to enrollment all parents / caregivers with be trained on how to put on the tDCS device. [name] will work with families having difficulty with placement or to help desensitize subjects to the tDCS equipment. Subjects will also be introduced to the EEG system and if needed, [name] will help participants feel comfortable with the headcap.
- Each subject will have their own tDCS device to use for the duration of the trial. All tDCS sponges are disposable and the system can be easily cleaned and stored between use by the parents. The tDCS will be returned to the Research Coordinator at subjects' completion of study. The tDCS headband can be cleaned with alcohol and placed in a sealed bag that is signed by cleaner / cleaning date. Study visits will be by video conferencing when possible. Equipment will be sent

- to subjects via Fed- Ex or courier. Rutgers University screening and testing procedures for prevention of CoVid19 will be followed.
- > A study staff will conduct the entire tDCS procedure and train the parents until the parent is fully able to apply the headset and use the device. Typically, this parent training is completed in approximately 30-mins through a review of a written instruction and modeling from the staff. The research assistant will also review the safety precautions with the parent, including instantaneous disconnection and proper power off procedures. Based on the 30,000+ sessions reported in the literature, tDCS was deemed safe, even in young children.
- > Then, the parent conducts the tDCS procedure under the supervision of the study staff (via telemedicine portal).
 - Once trained, the tDCS device will be placed on the subject by the parent. (Note that self-administration of tDCS is quite routine practice in other clinical applications of tDCS. In fact, the device we are using was developed specifically for home use.)
 - A member of the study team will observe the placement and removal of the tDCS device for each ABA session via video conferencing. The treatment will be discontinued when the child participant is crying (more than 5 min), is pulling at the device or equipment, or asking to stop, or if not participating in therapy. Information will be recorded on the treatment log.
- Parents and therapists will be instructed to monitor for redness under the electrode site and to keep the child from touching the area (i.e., cover with band aid). Any redness persisting greater than 2 hour or if there are any signs of skin abrasion/ lesion will be considered an adverse event reportable to the IRB.
- > tDCS will be suspended during illness such as viral illness with fever, if there are skin irritation requiring medical treatment or if the child is being evaluated for new neurological or medical conditions i.e., seizures / diabetes.
- Subjects may become be discharged from the study if there are changes in their medical history/ /medication treatment (ex. a new medication is prescribed that makes the participant ineligible). Following this training, the parent will be able to conduct the entire tDCS procedure independently. In certain cases that require additional assistance, a study staff will be available through the telemedicine portal to assist the parent during the sessions. We do not anticipate that many parents will require more than 1-2 training sessions

6.3bData/Safety Monitoring Board Details N/A

